9.3 Subgroup analyses

Both ORR and PFS will be evaluated for the following subgroups:

- ORR and PFS will be presented in subgroups defined by prognostic index scores, dichotomised as high risk and low risk as described in section 7.3.2.
- ORR and PFS will be presented by FcγR subgroups as described above.
- ORR and PFS will also be presented by duration of response (≤ 12 months or > 12 months) to previous treatment.
- ORR and PFS will also be presented by the number of prior therapy lines (as 1, 2, 3, or > 3).
- ORR and PFS will be presented for the category of patients with Follicular lymphoma (FL) or other indolent lymphoma (as one group).

In addition, PFS only will be presented in further subgroups as follows:

- Baseline ECOG status (0–1 vs. 2 or more)
- Age group (<65 vs. ≥ 65)
- Number of prior therapy lines (as 1, 2, 3, vs >3)

Statistical Analysis Plan Final Version 4.0

- Baseline NK cells number (<100 NK cells/ μl vs ≥ 100 NK cells/ μl)
- Baseline NK cells number (<100 NK cells/ μl vs. ≥ 100 NK cells/ μl): pooled analysis across all NHL subtypes (i.e., DLBCL, FL, MCL, other indolent NHL)
- Baseline NK cells number (<100 NK cells/ μl vs. ≥ 100 NK cells/ μl) split by DLBCL and FL+iNHL patients (FL+iNHL patients represent one group). Thus, MCL patients will be excluded from the analysis.
- Baseline CD16 expression ($< 60,000$ ABCs/NK cell) vs. $\geq 60,000$ ABCs/NK cell)
- Baseline CD16 expression ($< 60,000$ ABCs/NK cell) vs. $\geq 60,000$ ABCs/NK cell): pooled analysis across all NHL subtypes (i.e., DLBCL, FL, MCL, other indolent NHL)
- Baseline CD16 expression ($< 60,000$ ABCs/NK cell) vs. $\geq 60,000$ ABCs/NK cell): split by DLBCL and FL+iNHL patients (FL+iNHL patients represent one group). Thus, MCL patients will be excluded from the analysis.
- Rituximab refractoriness (Rituximab-refractory vs. not Rituximab-refractory; see definition below)
- Rituximab refractoriness (Rituximab-refractory vs. not Rituximab-refractory; see definition below): pooled analysis across all NHL subtypes (i.e., DLBCL, FL, MCL, other indolent NHL)
- Rituximab refractoriness (Rituximab-refractory vs. not Rituximab-refractory; see definition below): pooled analysis across all NHL subtypes excluding MCL (i.e., DLBCL, FL, other indolent NHL)

Rituximab refractoriness is defined as follows: no response (i.e., CR or PR) at all, or relapse within 6 months after completion of any rituximab-containing treatment regimen.

For the PFS subgroup analyses an estimate of the hazard ratio and a corresponding 95% confidence interval will be calculated using a Cox proportional hazards model with only one covariate in the model.

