4 BACKGROUND

4.1 Overview of Non-Hodgkin's Lymphoma

Non-Hodgkin's lymphoma (NHL) accounts for approximately 5% of all new cancer cases. Non-Hodgkin's lymphoma is a heterogeneous group of lymphoproliferative malignancies and is in 90% of cases derived of B cells.

Diffuse large B-cell lymphoma (DLBCL), an aggressive B-cell lymphoma, accounts for one-third of NHL, and after standard treatment with the anti-CD20 antibody rituximab with the chemotherapy CHOP (cyclophosphamide, doxorubicin, vincristin and prednisone) 30% to 40% of patients are still relapsed or refractory, requiring further treatment. Mantle cell lymphoma (MCL), like DLBCL, is an aggressive NHL but is far less responsive to treatment than DLBCL.

Follicular lymphoma (FL), an indolent B-cell lymphoma, accounts for 22% of NHL. Even if the overall response rate is high, standard therapy is rarely curative and nearly all patients will relapse. There is no standard-of-care treatment available for patients with advanced FL.

Therapy with a monoclonal antibody would have the potential to improve response rates and overall survival without increasing haematologic toxicity.

This is supported by initial data from other anti-CD19 monoclonal antibodies (MDX-1342 and SAR3419) and the bispecific antibody blinatumomab (Viardot, 2011), MDX-1342 a glycoengineered fully human anti-CD19 Ab (Camacho, 2009), SAR3419 a humanized IgG1 conjugated with DM4 (a cytotoxic maytansinoid derivate) (Coiffier, 2011) published preliminary data from their Phase I studies indicating that a CD19 is a valid target and that an anti-CD19 therapy has potential clinical benefit. No significant myelosuppression was reported from these trials.

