10.9.4 Immune Cells

For evaluation of the status of the immune system, B-, T- and NK cells in peripheral blood will be measured frequently throughout the study (exploratory assay) on sites selected for this assay by the sponsor. The absolute and percentage changes from baseline will be evaluated.

CD16 expression on NK cells in peripheral blood will be evaluated at baseline (exploratory assay).

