14.8 Biomarkers

Biomarker assessments will include expression levels of CD19 on malignant B cells, FcγRIIIa and FcγRIIIa genotyping, CD16 expression on NK cells, and B-, T- and NK cell counts.

In addition, the ADCC capacity of the patient will be assessed.

Due to the exploratory nature of these assays, the sponsor may decide at any point during the study to terminate these assessments, in which case the sites will be informed accordingly.

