Unless otherwise specified, Baseline is the last observation before the start of the study treatment, which is expected to be the Baseline Visit on Day 1, or Screening or any other unscheduled visits before the start of the study drug administration, if Baseline, Day 1 data are not available. For data such as CD16 expression on NK cells which is only recorded at Screening the Screening value will be the Baseline value, if the Screening value is missing then the baseline value will also be missing.

All data obtained on the eCRF and entered into the database will be provided in separate data listings showing individual patient values. The planning and reporting of statistical analyses will be carried out as described in the [REDACTED] SOPs.

Any patient who withdraws from the study will be analyzed with the data available. Imputation of missing values will not be performed, unless specified in the relevant sections of the SAP.

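### SAP 9.3 pools PFS hazard ratios over aggressive and indolent NHL without stratifying by subtype; a subtype-stratified hazard ratio beside each would be a cheap check

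*SAP*

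**What the plan says.** SAP 9.3 lists PFS subgroup contrasts by baseline NK count (cut at 100 cells/µl), baseline CD16 expression (cut at 60,000 ABCs per NK cell) and rituximab refractoriness. Each factor appears once without qualification and once as a "pooled analysis across all NHL subtypes (i.e., DLBCL, FL, MCL, other indolent NHL"). For refractoriness there is also a "pooled analysis across all NHL subtypes excluding MCL (i.e., DLBCL, FL, other indolent NHL"). For NK count and CD16 there is also a split into DLBCL and FL plus other indolent NHL.

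The hazard ratio and its 95% confidence interval are to be "calculated using a Cox proportional hazards model with only one covariate in the model". The SAP names no strata and no subtype adjustment.

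Protocol 4.1 describes DLBCL as aggressive and says that MCL "is an aggressive NHL but is far less responsive to treatment than DLBCL". It also says: "Follicular lymphoma (FL), an indolent B-cell lymphoma, accounts for 22% of NHL".

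Four other places matter:
- SAP 7.1 and 9.2 make presentation by subtype, for FL plus other indolent NHL, and overall the default.
- SAP 9.2 puts patient and event counts in the PFS Kaplan-Meier tables.
- Protocol 14.10 rules out inferential testing.
- Factor data may be incomplete. Immune cells are measured "on sites selected for this assay by the sponsor". Protocol 14.8 adds that "the sponsor may decide at any point during the study to terminate these assessments". For CD16, SAP 7.1 says that "if the Screening value is missing then the baseline value will also be missing".

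**The concern.** A one-covariate Cox model fitted to a mixed population compares everyone with the factor against everyone without it. Suppose the factor is commoner in the aggressive subtypes and those subtypes progress sooner. The group with the factor then has worse PFS even if the factor does nothing within any subtype. Both pools named above have this structure. Leaving out MCL does not remove it, because DLBCL is still combined with FL and other indolent NHL.

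What is at stake is how a few secondary tables are read. A pooled hazard ratio for CD16 or NK count will be taken as information about that biomarker, and SAP 1 allows planned analyses to go into study reports, regulatory submissions or manuscripts. If the imbalance is marked, part of the figure would reflect subtype mix.

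**Working it through.** **The plan's own figures.** The documents give no figure for these hazard ratios. Their only operating figures concern ORR, and both reproduce. The chance of fewer than 2 responses in 10 at a true ORR of 30% is 0.7^10 + 10 × 0.3 × 0.7^9 = 14.9%. The exact lower 95% limit for 9/30 is 14.7%. The point does not depend on either.

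**Inputs.** From the documents: the pools, the model, the aggressive and indolent labels, and cohorts of about 10 to 30 patients. Everything else is assumed: median PFS by subtype, factor prevalence, the fraction of patients with factor data, and the 30/10/30/10 cohort pattern (DLBCL/MCL/FL/other, as if two cohorts went on to Stage 2). There is no effect within any subtype unless stated.

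**By hand.** With exponential PFS, the hazard is inversely proportional to the median. Take 40 aggressive and 40 indolent patients, prevalence 70% v 40%, medians 3 v 6 months (relative hazard 2 v 1).
- With the factor: 28 aggressive and 16 indolent. Mean hazard (28 × 2 + 16 × 1)/44 = 1.64.
- Without it: 12 aggressive and 24 indolent. Mean hazard (12 × 2 + 24 × 1)/36 = 1.33.
- Starting hazard ratio: (72/44)/(48/36) = 1.23, where the true value is 1.

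**By simulation.** 4,000 trials per setting, exponential PFS, uniform censoring at 12 to 24 months, cohorts 30/10/30/10, complete data. Coverage is of the within-subtype value by the 95% interval. RMSE is on the log scale, unstratified v stratified.

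| Prevalence aggressive/indolent; medians (months) | By hand | Unstratified HR, coverage | Stratified HR, coverage | Rise in SE | RMSE |
|---|---|---|---|---|---|
| 50/50%; 3 v 6 | 1.00 | 1.00, 94.7% | 1.00, 95.1% | 6.4% | 0.243 v 0.261 |
| 55/45%; 3 v 6 | 1.07 | 1.07, 93.3% | 1.00, 95.1% | 6.8% | 0.253 v 0.258 |
| 60/40%; 4 v 6 | 1.08 | 1.08, 93.5% | 1.00, 94.5% | 8.3% | 0.256 v 0.264 |
| 70/40%; 3 v 6 | 1.23 | 1.22, 87.2% | 1.00, 95.6% | 11.8% | 0.314 v 0.268 |
| 70/40%; 2.5 v 9 | 1.42 | 1.40, 74.1% | 0.99, 94.9% | 11.5% | 0.416 v 0.281 |

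**Variations on the same five settings.**
- MCL excluded (30/30/10): unstratified 1.00, 1.06, 1.08, 1.21, 1.38, with coverage 95.1%, 94.1%, 93.8%, 89.2%, 78.8%. Stratified 0.99 to 1.00. SE rises 5-10%.
- Four cohorts of 10, complete data: unstratified 0.99, 1.07, 1.09, 1.21, 1.41. SE rises 13-19%.
- Cohorts 30/10/30/10, half of patients with factor data: SE rises 12-19%. In 21-33% of trials at least one stratum has a single factor level, against 0-3% with complete data. The unstratified RMSE is lower in four of the five settings, and higher only at 2.5 v 9 (0.51 v 0.44).
- Four cohorts of 10, half with factor data: SE rises about 28-35%. The unstratified RMSE is lower in every setting tried, for example 0.61 v 0.74 at 70/40%, 3 v 6.

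**MCL worse than DLBCL** (medians 2 v 3 months, indolent 6; 30/10/30/10, complete data): unstratified 1.08 with coverage 93.2% (55/45%) and 1.25 with 85.3% (70/40%). Stratified 1.00 in both.

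**A real effect, balanced prevalence** (true HR 0.5; 30/10/30/10): unstratified 0.50 (4 v 6), 0.52 (3 v 6) and 0.57 (2.5 v 9); stratified 0.49. The shift is small unless PFS differs strongly, and part of it is non-collapsibility of the hazard ratio and not confounding.

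**The case against.** The strongest case is that the SAP openly describes a univariable, descriptive hazard ratio and shows the by-subtype results next to it. That is largely right. The unqualified NK and CD16 entries in SAP 9.3, read with the by-subtype default and the patient and event counts in the Kaplan-Meier tables, give the numbers at each cut-off within each subtype. Refractoriness is also shown by subtype. A reader might infer that any imbalance would be hidden; the documents do not support this, and no extra cut-off table is needed. What the by-subtype results do not give is one pooled estimate controlled for subtype, and with 10 to 30 patients each is imprecise on its own.

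Second, the harm is hypothetical. A reader might infer that the pooled hazard ratios will be biased. The documents give no factor prevalence and no PFS by subtype, and Protocol 4.1 speaks of disease type and treatment responsiveness, not of PFS on this drug. The bias may be nil.

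Third, stratification can do worse overall. The RMSE figures bear this out for balanced, mildly unbalanced and sparse data. This counts against replacing the planned analysis, not against reporting both.

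Fourth, one covariate does not exclude strata, and SAP 1 and 4.1 allow unplanned analyses without an amendment. Nothing blocks the check, but it is not planned, and one chosen after the pooled result is seen carries less weight.

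**Conclusion.** The point stands as a minor one. The planned pooled hazard ratios for NK count, CD16 and refractoriness are open to confounding by subtype, and the plan contains no pooled estimate that controls for it. Under the assumed inputs the distortion is negligible with mild imbalance and becomes material only with strong imbalance, around 70% v 40% prevalence together with at least a twofold difference in median PFS. Whether the trial resembles either case cannot be told from the documents.

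Two stronger conclusions should not be drawn: that the planned hazard ratio is wrong, or that the stratified one should take its place. The contrasts are descriptive and secondary, there is no inferential testing, and the primary ORR analysis is untouched. Nothing is claimed about the pool of FL and other indolent NHL.

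**What to change.** In SAP 9.3, keep the planned unstratified hazard ratio. For the two pools that mix aggressive and indolent lymphoma (all subtypes, and all except MCL), report beside it a Cox hazard ratio stratified by NHL subtype, still with one covariate. State for each the number of patients with factor data, the number of events, and the number of strata that contain both factor levels. Label the stratified figure as a check on the planned one.

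The programming cost is one strata statement and a few extra columns, with no new data, because subtype is recorded for every patient. The statistical cost is the loss of precision set out above. It is heaviest if cohorts stop at 10 and NK or CD16 data are sparse, and the count of informative strata will show when the stratified figure is too thin to lean on.

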9.4 Other Efficacy Analyses

The ECOG performance status will be summarized categorically in a frequency table by visit.

10. PHARMACOKINETIC AND PHARMACODYNAMIC ANALYSIS

10.1 Pharmacodynamic Parameters Measured in Blood

Actual values and absolute and percent changes from baseline will be summarized descriptively by visit for the pharmacodynamic parameters B, T, and NK cell populations. Moreover, 95%

Statistical Analysis Plan Final Version 4.0

confidence intervals will be provided for mean and median changes in summaries of absolute changes from baseline and for median changes in summaries of percentage changes from baseline.

10.2 Pharmacodynamic Parameters Measured in Bone Marrow and Biopsy

At the Screening visit (Baseline), a bone marrow aspirate should be obtained. Results from bone marrow examination done within 4 weeks before screening are acceptable if the patient's disease has been stable since then. In this case only available data will be used and bone marrow examinations at screening for which this data are not available will not be repeated (e.g. for the sole purpose of CD19 expression).

Repeat of marrow aspirates and biopsies should be obtained at Day 28 of Cycle 2. Histological examination should be performed and the infiltration by malignant B-cells should be evaluated. Starting end of Cycle 3 and in the course of the follow up bone marrow examinations should only be repeated if response at last bone marrow examination was not CR.

On screening, CD19 expression of tumor cells in bone marrow will be determined by a central laboratory. In case CD19 expression on tumor cells can be measured in less than 15% of ITT patients the statistical analyses by baseline CD19 expression (as planned in the protocol) will not be performed. Data on baseline CD19 expression will only be listed. Other results from bone marrow aspiration and biopsy will not be available for statistical analysis.

10.3 Pharmacokinetic Analysis

10.3.1 Bioanalytical Assay of Pharmacokinetic Serum Samples.

MOR00208 concentration values (ng/mL) for each serum sample are to be processed using a validated Ligand Binding Assay. A separate bioanalytical phase plan and report will be generated that provide details on samples handling and processing, methods used for sample analysis, statements on quality control/quality assurance (QC/QA) and results of each individual sample analyzed for each patient by the bioanalytical labs.

All pharmacokinetic sample assessments will be performed at Eurofins ADME Bioanalyses, Vergèze, France.

10.3.2 Concentration Data

Pharmacokinetic concentration data will be listed as received from the bioanalytical laboratory and as used to estimate the PK parameters. The PK concentrations will be summarized based

on nominal (scheduled) sampling times. Concentration figures (linear and log y-axis) for each patient will be presented, as well as mean concentrations.

Any concentrations outside allowable windows will be excluded from summary statistics.

Allowable windows are:

± 15 min for the samples at the end of infusion and 1h after the end of infusion, ± 30 min for the sample 4h after the end of infusion, and ± 2 h for the sample 24 h after the end of infusion. In addition, concentrations will be considered outside allowable windows if infusions after the first infusion took place outside a ± 1 day window within a 28 day cycle.

Furthermore, PK samples which were analyzed outside the formally validated long-term stability will be flagged and excluded from summary statistics.

For pharmacokinetic parameter estimation, analyte concentrations that are below the limit of quantification (BLQ) will be assigned a value of zero when they precede the first quantifiable sample. The WinNonlin program automatically does this for the predose sample as it disregards any concentrations reported before the first administration of study drug.

All other BLQ samples will be treated as missing data.

When 2 or more BLQ sample values occur consecutively, all remaining concentration values will be set to missing.

No linear interpolation for these missing concentration values will be completed.

10.3.3 Pharmacokinetic Parameters estimated

Individual PK parameters will be estimated for each patient in the PK population as data permits. Pharmacokinetic parameter estimates will be completed using WinNonlin (Pharsight Corporation). Descriptive summaries (mean, SD, %CV, median, minimum, and maximum) of concentrations at each scheduled time-point and the determined or calculated PK parameters will be presented. For patients receiving maintenance treatment after cycle 3, the FU1, FU2 and FU3 visits will be excluded from PK summary statistics, since the concentrations of MOR00208 at the FU1, FU2 and FU3 visits may be influenced by additional MOR00208 doses in maintenance treatment. The categorical variable t_{\max} will only report median, minimum and maximum.

The following PK parameters have been initially identified as important for the analysis of PK. Additional PK parameters may be required. The SAP will not be amended for additional PK

parameters unless the PK analysis is significantly altered. If the SAP is not amended, any additional PK parameters will be described in the CSR.

The following PK parameters are to be computed for each patient as data permit on samples obtained.

Parameter	Units	Description and Calculation Method
Parameters Estimated from the First Dose		
C_{pd}	$\mu\text{g/mL}$	Predose serum concentration observed
C_{max}	$\mu\text{g/mL}$	Maximum serum concentration observed
C_{last}	$\mu\text{g/mL}$	Last quantifiable concentration from the First Dose
t_{max}	hr	Time to maximum serum concentration observed
AUC_{0-last}	$\text{hr} \times \mu\text{g/mL}$	Area under the concentration curve from dose time zero (0) to the time the last quantifiable concentration is observed.
Parameters Estimated from the Last Dose		
λ_Z	1/hr	Apparent terminal rate constant calculated from the regression analysis slope of the log-transformed concentrations included in the terminal phase of the concentration-time curve from the last dose
$t_{1/2}$	hr	Apparent terminal half-life calculated as $\ln(2)/\lambda_Z$

The parameter estimates dependent upon the regression analysis of the terminal phase (λ_Z , $t_{1/2}$) will only be reported for those patients where a sufficient and meaningful number of serum concentration values are available. All possible values will be calculated and listed with a flag to indicate inclusion in the summary. Only those values that pass the following criteria will be included in the summaries:

All regression analyses must contain a minimum of 3 concentrations and characterize a descending concentration. The estimate of λ_Z from the regression analysis must have a correlation coefficient $R^2 > 0.80$ to be accepted. If these conditions fail then λ_Z and $t_{1/2}$ will be listed but not reported in the summary table.

The parameters λ_Z and $t_{1/2}$ will not be calculated for patients receiving maintenance treatment after cycle 3 if they receive any dose after the FU1 visit, since the concentrations of MOR00208 at the FU2 and FU3 visits may be influenced by additional MOR00208 doses in maintenance treatment and thus not suited to estimate these parameters. However, if patients receive maintenance treatment after cycle 3 but have blood samples taken at the FU1, FU2, and FU3 visits with no doses administered between them, then those samples may be used for estimating these parameters.

11. SAFETY AND TOLERABILITY ANALYSES

The analysis of safety assessments in this study will include summaries of the following categories of safety and tolerability data collected for each patient:

- Adverse Events
- Clinical Laboratory Investigations (Blood Chemistry, Hematology, Coagulation, Urinalysis, anti-MOR00208 antibodies)
- Vital Signs (Blood Pressure, Heart Rate, Respiratory Rate, Body Temperature)
- Electrocardiogram (ECG) Investigations
- Physical Examination
- Measurements of exposure

11.1 Adverse Events

The primary safety endpoint is the incidence and severity of adverse events (AEs). This endpoint will be determined based on the Safety Population. If not specified otherwise, the adverse events summary and overall table will be displayed overall, by each NHL subtype, and for the combined group of FL and other indolent NHL.

All adverse events (AEs) and serious adverse events (SAEs) will be coded using the Medical Dictionary for Regulatory Activities (MedDRA), Version 20.1.

Treatment emergent AEs are defined as AEs occurring or worsening after the start (date and time) of the first study treatment and up to 30 days after the last study treatment including all treatment cycles (treatment emergent period). However, adverse events occurring or worsening later than 30 days after the last treatment are defined as treatment emergent if these are considered to be related to the study drug.

If the start date and time of an AE are partially or completely missing, the AE will be assumed to be treatment-emergent if it cannot be definitely shown that the AE did not occur or worsen

during the treatment emergent period (worst case approach). Missing dates and times will not be replaced.

Thus, the following approach will be taken:

- If the start time of an AE is missing but the start date is complete, an AE will only be excluded from treatment emergent AEs if start day is before day of first treatment or start day is after end day of treatment emergent period.
- If start time and day are missing but the start month is complete, an AE will only be excluded from treatment emergent AEs if start month is before month of first treatment or start month is after end month of treatment emergent period or if stop date/time is before start of first treatment.
- If start day and months are missing but the start year is complete, an AE will only be excluded from treatment emergent AEs if start year is before year of first treatment or if start year is after end year of treatment emergent period or if stop date/time is before start of first treatment.
- If start date is completely missing, an AE will not be excluded from treatment-emergent AEs unless the stop date/time is before start of first treatment.

Time from first treatment to onset of AE [days] will be calculated for complete dates only and will be included in listings.

An AE summary table will be presented showing the incidence and frequency of any

- Treatment-emergent AEs (TEAEs)
- Serious Adverse Events (SAEs)
- Serious Adverse Events (SAEs) related to MOR00208
- MOR00208-related TEAEs
- MOR00208-related TEAEs by toxicity (according to NCI-CTC toxicity criteria)
- MOR00208-related TEAEs by severity
- Infusion related TEAEs
- TEAEs leading to any action on MOR00208
- TEAEs leading to discontinuation of MOR00208
- TEAEs leading to death

Statistical Analysis Plan Final Version 4.0

The incidence refers to the number and percentage of patient with at least one TEAE of the specified type and the frequency to the number of AEs.

The analyses by toxicity will be based on the NCI-CTC grade (per National Cancer Institute Common Toxicity Criteria, version 4.0). If the NCI-CTC grade is not available, this will be analyzed as “Missing”.

Summaries of incidence rates (number and percentage of patients) and frequencies (number of AEs) of individual TEAEs by MedDRA System Organ Class (SOC) and Preferred Term will be prepared overall and by NHL subtype. Such summaries will be displayed for all

- TEAEs
- TEAEs by toxicity according NCT-CTC
- TEAEs by severity
- TEAEs suspected to be related to MOR00208
- TEAEs leading to discontinuation of MOR00208
- Infusion related TEAEs
- Cytokine release syndromes
- Treatment-Emergent Serious Adverse Events
- TEAEs suspected to be related to MOR00208
- Serious Adverse Events suspected to be related to MOR00208 (Serious Adverse Reactions)
- TEAEs of toxicity grade 3 or higher
- MOR00208-related TEAEs of toxicity grade 3 or higher
- TEAEs of special interest (ie, infusion-related reactions of grade 3 or higher, cytokine release syndrome, allergic reaction to MOR00208 of grade 3 or higher and overdoses)
- Haematological Treatment Emergent Adverse Events
- Overdoses (defined as exceeding planned dose by more than 10%)
- Death cases (irrespective of death due to progressive disease or other reason)
- Pre-treatment AEs (based on all Screened Patients instead of the Safety Population)

A summary of all TEAEs will also be provided by FcγR polymorphisms.

In these summaries each patient will be counted only once within each preferred term to calculate the incidences.

AE listings of all adverse events with the following details will be provided for

- AEs – details
- AEs – action taken
- AEs – coding details

In the AE listings, AEs that started prior to the administration of any study drug will be flagged as pre-treatment AEs. AEs that start 30 days after the last study treatment including all treatment cycles will be flagged as post-treatment AEs.

Special AE summary listing displaying details of the event(s) captured on the eCRF in a compact format will be provided for

- AEs leading to death
- AEs leading to discontinuation of MOR00208
- AEs of toxicity grade 3 or higher
- Infusion related TEAEs
- Serious Adverse Events
- Death cases (irrespective of death due to disease progression or other reason)

Serious adverse event reconciliation will be performed as detailed in the SAE reconciliation plan.

The number and percent of patients with at least one pretreatment AE will be summarized by NHL subtype and by system organ class and preferred term.

